# 8.6.3 Exploratory endpoints

•Time from randomisation to

oConfirmed hospital admission for congestive heart failure oConfirmed hospitalisation for unstable angina

- oConfirmed coronary, cerebrovascular or peripheral revascularization
- Medical resource utilisation during the study (e.g. hospitalisations, outpatient physician visits, medication use) as measured by participant / GP questionnaires

# 9 Selection and withdrawal of participants

# 9.1 Inclusion Criteria

To be included in the study the participant must meet all of the following criteria:

- •Understand the study procedures, alternative treatments available, and the risks involved with the study, and voluntarily agree to participate by providing written informed consent
- Age ≥ 40 years
- •HbA1c  $\geq$  36.6mmol/mol but <47.5mmol/mol; measured within one year prior to enrolment
- •Estimated 10-year CVD risk ≥20% as assessed by the Framingham or QRISK2 scores; laboratory values used for the risk calculators should be collected no more than one year prior to enrolment.
- •Estimated glomerular filtration rate (eGFR) ≥45ml/min as determined by the MDRD-4 method; measured within 6 months prior to enrolment
- Participant agrees to allow study staff to contact his or her General Practitioner and/or consultant to notify them of study participation and to obtain all medical records necessary for complete data ascertainment during the follow-up period (including recording of NHS number and access to Health Episode Statistics (HES))
- •Participant agrees to be tagged for mortality with the Office for National Statistics and to be tagged for
  - •Time to first non-melanoma cancer diagnosis (supplied by National Cancer Registry)
  - •Death due to a non-melanoma cancer cause according to primary/underlying cause of death on death certificate (supplied by the
    - Office of National Statistics)

# 9.2 Exclusion Criteria

- The participant may not enter the study if ANY of the following apply:
- Unable to provide written consent
- Prior history of physician-diagnosed T2DM. NOTE: Participants with a history of gestational diabetes which resolved after pregnancy are permitted to enrol.
- Prior history of CVD, defined as:
  - myocardial infarction, surgical or percutaneous coronary revascularization procedure
  - Stroke (haemorrhagic or ischaemic) NOTE: Participants with prior transient ischaemic attack or unstable angina are NOT excluded and may be enrolled
- Participant has a planned or anticipated coronary revascularisation procedure within 6 months following enrolment

*NOTE: Participants with previous peripheral revascularisation procedure are NOT excluded and may be enrolled* 

- Participant is breastfeeding or known to be pregnant
- Participant is currently taking metformin (for any reason) or they have taken metformin in the last three months
- History of cirrhosis of the liver or other significant hepatic impairment, as assessed by medical history
- End-stage renal disease (CKD stage 3b or worse, eGFR<45ml/min)
- In the investigator's opinion, participant has a medical history that indicates a life expectancy of <2 years or might limit the individual's ability to take the study treatments for the duration of the study
- Any other significant disease or disorder which, in the opinion of the Investigator, may either put the participant at risk because of participation in the study, or may influence the result of the study, or the participant's ability to participate in the study.

• Participant is enrolled in or has participated within 12 weeks prior to enrolment in another experimental protocol involving the use of an investigational drug or device or an intervention that would interfere with the conduct of the study

#### 9.3 Treatment Assignment, Randomisation Number and Method of Unblinding

A sequence of unique Randomisation Numbers will be generated for each study site by a nominated Oxford DTU statistician. This statistician (with no involvement otherwise in GLINT) will in strict confidence randomly assign treatment allocation codes for *metformin prolonged release tablets* or *placebo* 1:1 to each Randomisation Number, blocked within site. Prior to Trial Management System Database lock the Randomisation Numbers and their respective treatment allocation codes will be provided in strict confidence only to a nominated Oxford DTU senior applications programmer and to the IDMC independent statistician. The nominated programmer will store them in the encrypted Medication & Codebreak Database with access only being available for a single participant at a time and only to staff authorised to unblind assigned study medication as described in section 9.5.

A secure system will automatically produce medication distribution lists detailing which study medication packs should be sent to which participants. This system will identify from the Trial Management System Database which participants will be requiring titration or maintenance packs. It will then utilise the encrypted Medication & Codebreak Database to allocate the next available pack that has a Treatment Code which matches the Treatment Code allocated to the participant's Randomisation Number. Finally, it will access the encrypted Contact Database to acquire the participant contact details required for the mailing label.

Immediately after Trial Management System Database lock the Oxford DTU Informatics group will incorporate the treatment allocation codes into the Trial Management System Database so that unblinded data can be made available for analysis.

The Randomisation Numbers alone, *i.e.* without the treatment allocation codes, will be added to Trial Management System for allocation to participants eligible for randomisation.

# 9.4 Method of Blinding

The study uses a double-blind design, neither the participants nor GLINT personnel will know which treatment the participant is taking. The IMP will have the same visual appearance as the placebo.

#### 9.5 Emergency Unblinding

The study phone line can be used to unblind participants to the randomised treatment assignment only if deemed clinically essential by those with responsibility for providing health care to the participant and the duty study clinician, that is to say in a situation in which the responsible clinician considers that the treatment received in the study needs to be identified in order to appropriately manage the participant's presenting condition. Drug identification information is to be unmasked ONLY if necessary for the welfare of the participant and will only be undertaken by those with appropriate delegated authority. All participants will be provided with a study contact card to present to any clinician that may treat them. The study card will have details of the 24 hour phone line (details of which will also be included on other key documents such as the Participant Information Leaflet). The 24 hour telephone number will be available during office hours, and by a study clinician outside of office hours, who will be able to unblind a participant if required. It is the responsibility of the Investigator or the team member

who completes the unblinding to promptly document and explain any unblinding to the Sponsor as per SOP.

The unblinding system is accessed electronically via the trial management system and can be accessed 24 hours a day. Any occurrence of an unblinding event will be recorded in the web-based electronic trial management system, which records the time, date and operator as well as the reason for unblinding, but not the allocated treatment. The study Sponsor will be informed of any unblinding occurrences. The data required to break the code are, however, stored in the separate encrypted Medication & Codebreak Database and only accessible to the site investigators or the 24 hour phone line team members.

The GLINT team at the MRC Epidemiology Unit, University of Cambridge will operate the phone line. The phone line will also be available to answer urgent clinical questions from sites concerning enrolled participants (adverse events, unblinding etc.) as well as questions to determine whether a particular participant qualifies for enrolment. Each site will have site-specific phone lines for participant queries to be manned during normal office hours.

## 9.6 Changes in participant study status

Optimally, all participants should remain on study treatment and follow up for the duration of the study. However, it is recognized that in rare instances a participant may temporarily or permanently discontinue study medication or participation in the study.

Discontinuations from the study occur only if the participant explicitly withdraws consent for all forms of follow up.

# 9.6.1 Discontinuation of study medication

Discontinuations from study treatment may occur for protocol-specified reasons (see below), due to the judgment of the primary investigator, or due to the participant's decision.

Protocol specified reasons for study drug discontinuation are:

• An adverse event which requires discontinuation of the study medication or results in inability to continue to comply with study procedures. Study drug can be resumed if the event resolves.

• Participant refuses follow up via participant annual questionnaire

• Development of chronic kidney disease (CKD stage 3b or worse, eGFR<45ml/min).

•Participant is temporarily not contactable

Participants are considered temporarily not contactable in the following situations:

- •Telephone contacts are made at 4 and 8 weeks. Sites will make three attempts to call the participant during this period. After three failed call attempts the participant is lost to follow up and the drug supply is stopped.
- •The participants are asked to complete and send a questionnaire at 4 months, then annually. Failure to return the questionnaire will result in a repeat issue of the questionnaire at 4 weeks after the due date and also at 8 weeks if required. Continued failure to return the questionnaire within another month results in an attempt to call the participant. After three failed call attempts the patient is lost to follow up and the drug supply is stopped.

For participants who fulfil the above criteria, attempts will be made annually to reestablish contact. If contact is re-established and the participant agrees, the drug will be re-started.

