#### Note:

Participants who develop T2DM during the course of the study should be advised to continue taking study medication and their GP will be advised to consider adding either metformin, such that the daily dose does not exceed the permitted maximum, assuming the study medication is the active therapy (see Table 1), or an alternative glucose lowering drug if required.

GLINT study medication daily dose	Maximum additional daily amount of standard release metformin permitted	Maximum additional daily amount of prolonged release metformin permitted
500 mg (1 tablet)	2000 mg	1500 mg
1000 mg (2 tablets)	1500 mg	1000 mg
1500 mg (3 tablets)	1000 mg	500 mg

Table 1: Prescription of additional metformin for those developing T2DM during the study

Participants who become pregnant during the course of the study can continue taking study medication (28).

Participants who experience a possible CVD event during the study will be encouraged to continue taking study medication as long as there are no contraindications.

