#### 10.4 Dosage modifications

During the treatment period, randomised participants will receive study medication by post in 16-weekly batches. For the first batch following randomisation, individuals will be advised to take 1 tablet/day (500mg metformin prolonged release/placebo) for four weeks, titrating up to 2 tablets/day for weeks 5 to 8, and 3 tablets/day thereafter. Participants will receive a phone call four and eight weeks after randomisation to confirm titration competency. Participants will have contact details of their local research team and the emergency telephone number should they have any queries or experience any serious side effects. Any participants who cannot tolerate 1500mg/day will be advised to take the highest tolerated dose, this will be determined during the titration calls and at the 3 and 6 month visits. Participants will be expected to continue taking study medication for the duration of the study.

Participants that have moderate renal impairment (chronic kidney disease stage 3a estimated glomerular filtration rate [eGFR] 45-59 ml/min/1.73m^2) recorded during their participation will be recommended a maximum daily dose of 1000mg metformin prolonged release/placebo.

During the feasibility phase, research staff will telephone the first 10 participants recruited in each site to enquire as to receipt of the study drug. The DTU will use information from these calls to monitor for any critical failures in the drug delivery process and if they occur will devise an action plan to address underlying causes.

Following completion of the feasibility phase, participants will not be asked to attend any further research visits / health assessments beyond the baseline visit, and will be followed up by post.

If the participant experiences episodes of hypoglycaemia, they will be advised to downtitrate their dose. If they continue to experience hypoglycaemic episodes they will be advised to discontinue the study medication.

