#### 10.7 Concomitant therapy

Concomitant medications will be used at the discretion of the participant's usual care provider, who will be informed of the participant's enrolment in the study and the use of blinded study medication. Open label use of metformin is contraindicated during the study except for those participants who develop T2DM during the study where up to a maximum of 1g/day (Table 1) can be prescribed in conjunction with continued study medication.

Any current prescribed medication, other than the study medication, will be recorded at the baseline visit following information from the participant. This information will be updated following receipt of annual questionnaires sent to the participant's GP.

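### The mandatory re-start of study drug in 9.6.1 is not linked to the Table 1 metformin limits, which do not cover a participant who is off study drug

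*Protocol*

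**What the plan says.** **Re-start after lost contact (Protocol 9.6.1).** Participants become temporarily not contactable through failed titration calls or through unreturned questionnaires. On the questionnaire route, two re-issues come first; then "Continued failure to return the questionnaire within another month results in an attempt to call the participant", and three failed calls stop the supply. After that, "attempts will be made annually to reestablish contact". The rule on success is: "If contact is re-established and the participant agrees, the drug will be re-started".

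**Resumption after an adverse event (same section).** "Study drug can be resumed if the event resolves".

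**Added metformin (Note and Table 1 in 9.6.1).** Participants who develop type 2 diabetes (T2DM) are to be advised to stay on study medication. The GP is advised to consider another glucose-lowering drug or extra metformin, the latter "such that the daily dose does not exceed the permitted maximum, assuming the study medication is the active therapy". Table 1 has rows for one, two and three study tablets and none for zero.

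**Concomitant therapy (10.7).** Open-label metformin is contraindicated except after incident T2DM, where "up to a maximum of 1g/day (Table 1) can be prescribed in conjunction with continued study medication". On the record of prescribed medication, "This information will be updated following receipt of annual questionnaires"; these go to the GP.

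**Dose (10.4).** The step-up is written for the start of the trial: "For the first batch following randomisation, individuals will be advised to take 1 tablet/day" for four weeks, then two tablets in weeks 5 to 8, then three. No re-start dose is given.

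**The concern.** The re-start sentence is mandatory and names two conditions, renewed contact and agreement. It does not ask whether the participant has begun metformin meanwhile, give a re-start dose, or require that the GP be told.

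Because re-contact is tried once a year, the gap can last about a year or longer. This population is enrolled for raised glucose, and incident T2DM is a secondary endpoint, so a diagnosis in the gap is plausible. A GP treating a patient who is no longer taking study tablets finds no row for that situation in Table 1, and 10.7 sets its cap only alongside continued study medication. If study drug is then posted again, nobody is required to compare the two doses.

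What is at stake is the safety of active-arm participants. The protocol guards comparable starts: metformin use currently or in the last three months bars entry (9.2), and renal function must be rechecked before the drug is reinstituted after contrast (10.3).

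**Working it through.** **Inputs.** Table 1 (9.6.1); maximum study dose 1500 mg/day, three 500 mg tablets (10.1.1); titration steps (10.4); the 1 g/day cap (10.7).

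**Step 1. Ceiling implied by Table 1** = study dose + maximum additional dose. It is implied by the table and not printed there.

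| Study tablets | Standard release added | Prolonged release added |
|---|---|---|
| 1 | 500 + 2000 = 2500 mg | 500 + 1500 = 2000 mg |
| 2 | 1000 + 1500 = 2500 mg | 1000 + 1000 = 2000 mg |
| 3 | 1500 + 1000 = 2500 mg | 1500 + 500 = 2000 mg |

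The sums are constant, so the ceilings are 2500 and 2000 mg/day.

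**Step 2. Open-label dose above which re-start exceeds the ceiling** = ceiling − study dose. At three tablets: 2500 − 1500 = 1000 mg standard release; 2000 − 1500 = 500 mg prolonged release.

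**Step 3. Totals in the active arm after re-start at three tablets.** The protocol gives no open-label dose for someone off study drug, so 500 to 2500 mg/day is an assumed range.

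| Open-label dose | Total | Against 2500 (standard) | Against 2000 (prolonged) |
|---|---|---|---|
| 500 mg | 2000 mg | within | at limit |
| 1000 mg | 2500 mg | at limit | over by 500 |
| 1500 mg | 3000 mg | over by 500 | over by 1000 |
| 2000 mg | 3500 mg | over by 1000 | over by 1500 |
| 2500 mg | 4000 mg | over by 1500 | over by 2000 |

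**Step 4. If the first-batch titration were reused.** One tablet exceeds only above 2000 mg standard or 1500 mg prolonged release. Two tablets (weeks 5 to 8) exceed above 1500 or 1000 mg. Three tablets follow from week 9. For open-label doses that Table 1 lists (up to 2000 mg standard, 1500 mg prolonged), an excess could therefore not begin before week 5.

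**Step 5. 10.7 against Table 1.** A flat 1000 mg is above the Table 1 limit for prolonged release with three tablets (500 mg). It equals the limit for standard release with three tablets and prolonged release with two. It is below the limit in the other three cells (2000 and 1500 mg standard; 1500 mg prolonged). Following 10.7 literally with three tablets and prolonged release gives 1500 + 1000 = 2500 mg, 500 mg over the 2000 mg ceiling, with no interruption of study drug needed.

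**The case against.** The strongest case against is that 9.6.1 should not be read apart from rules that remain in force.

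- Participants who stop the drug stay in the study and are still sent questionnaires (Appendix 1, footnote 5). The Note speaks of anyone developing T2DM during the study and tells the GP to assume active drug.
- The GP is told of enrolment and of what to do if T2DM develops (10.7, 11.2). A GP who keeps to the three-tablet row produces no excess.
- The annual GP questionnaire covers T2DM and current medication, and a reported secondary endpoint triggers immediate collection of information (11.3.1).
- Section 12.2.1 bars further study drug once eGFR is below 45.
- Resumption after an adverse event is permitted, not required, and those participants need not have lost contact.
- The harm needs a chain: diagnosis in the gap, a prescription above the three-tablet row, re-start at a high enough dose, and nobody noticing.

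Most of this stands, and it is why the risk is conditional. A reader might infer that contact and agreement are the only safeguards in the whole protocol. They are the only conditions in the re-start sentence, but the controls above exist elsewhere.

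The objection does not close the gap. None of these controls is tied to the re-start decision. The Note is framed around a participant who continues study medication. The renal bar does not detect metformin. GP medication data may be many months old, and on the questionnaire route the participant's own form is missing by definition.

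**Conclusion.** The point holds as a conditional dosing-safety gap worth correcting. The re-start rule is not linked to Table 1, and neither Table 1 nor 10.7 covers a participant who is off study drug. Following the text exactly can put an active-arm participant above the implied 2500 or 2000 mg/day ceiling. At three tablets this needs open-label metformin above 1000 mg standard release or 500 mg prolonged release; the size of any excess depends on an open-label dose the protocol does not give.

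The inconsistency between 10.7 and Table 1 is separate and does not depend on that chain.

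Two stronger readings are not supported. A reader might turn the rows in Step 3 into a proportion of participants at risk, but they are dose combinations, and the documents give no frequency for any link in the chain. A reader might also infer damage to the trial result; nothing here bears on the efficacy comparison, the event count or power.

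**What to change.** **In 9.6.1 add:** *Before study medication is re-started or resumed, current metformin use and the most recent available eGFR will be checked with the participant and, if needed, the GP. Study medication will be re-started, using the section 10.4 titration, only up to the number of tablets Table 1 permits with that metformin dose and within the renal limits of sections 10.1.1 and 12.2.1. The GP will be told of the re-start.*

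Read in this direction, Table 1 gives:

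| Most tablets at re-start | Standard release already taken | Prolonged release already taken |
|---|---|---|
| 3 | up to 1000 mg | up to 500 mg |
| 2 | up to 1500 mg | up to 1000 mg |
| 1 | up to 2000 mg | up to 1500 mg |
| none | above 2000 mg | above 1500 mg |

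The renal limits then apply on top: at most two tablets (1000 mg) at eGFR 45–59 and none below 45.

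**In 10.7** replace the flat 1 g/day with *up to the limits in Table 1*, and do not confine those limits to time on study drug. Confining them would expressly leave the off-drug interval uncovered.

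**Cost.** A short check at a contact already being made, a note to the GP, and some participants re-starting on fewer tablets or none. The rule is the same in both arms and keeps the blind. The annual GP questionnaire already asks for the latest eGFR (section 6), so no new visit or data system is needed.

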#### Note:

Participants who develop T2DM during the course of the study should be advised to continue taking study medication and their GP will be advised to consider adding either metformin, such that the daily dose does not exceed the permitted maximum, assuming the study medication is the active therapy (see Table 1), or an alternative glucose lowering drug if required.

GLINT study medication daily dose	Maximum additional daily amount of standard release metformin permitted	Maximum additional daily amount of prolonged release metformin permitted
500 mg (1 tablet)	2000 mg	1500 mg
1000 mg (2 tablets)	1500 mg	1000 mg
1500 mg (3 tablets)	1000 mg	500 mg

Table 1: Prescription of additional metformin for those developing T2DM during the study

Participants who become pregnant during the course of the study can continue taking study medication (28).

Participants who experience a possible CVD event during the study will be encouraged to continue taking study medication as long as there are no contraindications.

